6.2.4 Previous and Concomitant Medications

Previous and concomitant medications will be summarized by therapeutic subgroup (ATC 2nd level) and chemical subgroup (ATC 4th level) and preferred WHO name by treatment group for the SAF. Subjects taking the same medication multiple times will be counted once per medication and investigational period.

Previous medications are defined as medications that patients started prior to first administration of study medication. Concomitant medications are defined as any medications that subjects took after the first dose of study medication and either up to 30 days from last dose of study drug, or first dose of study drug during the active treatment extension period, whichever comes sooner. Medications that started prior to first administration of study drug and continued while study drug was given will be counted in both previous and concomitant medications.

6.3 Study Drug Exposure and Compliance

Duration and compliance of study drug will be summarized for SAF by treatment group and overall.

Number and percentages of subjects with the following categories of study drug duration will be summarized: >0 to ≤ 1 days, >1 to ≤ 7 days, >7 to ≤ 14 days, >14 to ≤ 21 days, >21 to ≤ 28 days, >28 to ≤ 42 days, >42 to ≤ 56 days, >56 to ≤ 84 days, and >84 days.

Number and percentages of subjects with the following cumulative categories of study drug duration will be summarized: $\geq 1 \text{ day}$, $\geq 7 \text{ days}$, $\geq 14 \text{ days}$, $\geq 21 \text{ days}$, $\geq 28 \text{ days}$, $\geq 42 \text{ days}$, $\geq 56 \text{ days}$ and $\geq 84 \text{ days}$.

Overall treatment compliance with the dosing schedule will be examined for subjects in the SAF whose total study drug count and first and last days of treatment are known. Compliance will be calculated compared to the actual treatment period of dosing (first to last day of the double-blind treatment period), not to the planned treatment period.

Percent overall compliance over the 12-week double-blind treatment period will be summarized in two ways for the SAF:

- Descriptive statistics will be presented by treatment group.
- Percent compliance will be categorized according to the following categories by treatment group:
 - < 50%,

 - $\circ \geq 50\%$ to < 85%,
 - $\circ \quad \geq 85\% \text{ to} < 120\%,$
 - $\circ \geq 120\%$, and
 - Unknown.

Overall treatment compliance through Week 4 (study day 28 of exposure) will be analyzed in a similar manner.

To explore the impact of the COVID-19 pandemic, additional analysis will be performed by excluding the days of missing study drug/drug interruption due to COVID-19 in the duration and compliance calculation, according to the study drug interruption CRF page.

6.4 Analysis of Efficacy

All statistical comparisons will be conducted using 2-sided tests at the $\alpha = 0.05$ significance level unless specifically stated otherwise. There are additional testing details below regarding the 4 co-primary endpoints. All null hypotheses will be of no treatment difference, all alternative hypotheses will be 2-sided and control for 2 comparisons to placebo using the Hochberg approach, unless specifically stated otherwise.

The family-wise type I error rate for the 2 active dose groups compared to placebo for the 4 co-primary efficacy endpoints will be controlled using a Hochberg approach. All 4 co-primary endpoints must be statistically significant for a given dose to be considered successful. Given that, the largest p-value in each dose group will be used to test that dose because it represents the least significant of the co-primary endpoints.

If the larger of the two maximum p-values, one from each dose, is less than 0.05, then both dose groups are considered statistically significant. If not, then if the smaller of the p-values is less than 0.025, the second compared dose is considered statistically significant. Othewise, neither dose is considered statistically significant. The trial will be considered successful if at least one dose is statistically significant.

All analysis of efficacy will be presented by treatment group for FAS, unless specified otherwise.

In general, the mechanism of missing data due to COVID-19 will be assumed to be missing at random (MAR).

6.4.1 Analysis of Primary Efficacy Endpoints

6.4.1.1 Primary Analysis for Primary Efficacy Endpoints

For each of the 4 co-primary efficacy endpoints, a mixed models repeated measures analysis of covariance (MMRM) will be used with treatment group, week (Week 1 through Week 12) and smoking status (current vs former/never) as factors, with baseline weight and baseline VMS as covariates, as well as an interaction of treatment by week and an interaction of baseline measurement by week. An unstructured covariance structure shared across treatment groups will be used to model the within-patient errors (and then Toeplitz if model does not converge). The Kenward-Roger approximation will be used to estimate denominator degrees of freedom and adjust standard errors. This analysis will use a restricted maximum likelihood-based repeated-measures approach. The treatment difference will be estimated at all study weeks (subtract placebo change from baseline from each fezolinetant response). MMRM will use all available on-treatment data to inform mean treatment effect estimates without requiring explicit imputation for missing data due to intercurrent events (i.e., for discontinued subjects). This approach is consistent with the hypothetical strategy used for the estimand, which is to compare subjects as though they had continued on the assigned treatment. Given the primary objective of the study, the analysis should describe the pharmacologic effect of the randomized treatments. The MMRM approach, and the missing at random (MAR) assumption, allows us to hypothesize that subjects had continued on assigned treatment while not being influenced by how subjects might have done without treatment or with alternative treatment(s).

Comparisons between the fezolinetant and placebo at Week 4 and Week 12 will be calculated based on least-squares mean contrasts using a 2-tailed 95% confidence interval (CI) and p-values. The LS Means will be estimated using weights proportional to the percentage of women who were randomized as current smokers. Details regarding determination of statistical significance can be found in Section 6.4

The hypothesis for each pairwise comparison is given as follows:

H0: The change from baseline at week 4 (or 12) for fezolinetant and placebo are the same

H1: The change from baseline at week 4 (or 12) for fezolinetant and placebo are not the same

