¹⁴C-ESN-364 ADME: absorption, disposition, metabolism and excretion of ¹⁴C-ESN-364; MAD: multiple ascending dose; MR-VMS: menopause-related vasomotor symptoms; SAD: single ascending dose; VMS: vasomotor symptoms

Source: Fezolinetant (ESN364) Investigator's Brochure

In patients, study ESN364_HF_204 was a 12-week double-blind, placebo-controlled, parallel-group, multicenter, proof of concept study to assess the effect of 12-week administration of fezolinetant in early postmenopausal women suffering from HFs. A total of 80 patients, 40 in each treatment group, completed the entire study. In this study, the mean HF frequency for the moderate and severe VMS at weeks 4 and 12 reduced by approximately 88% and 93% from baseline compared to a placebo decrease of 38% and 46%, respectively (P < 0.001). The mean HF score for the moderate and severe VMS at weeks 4 and 12 dropped approximately 89% and 94% from baseline compared to a placebo decrease of 38% and 46%, respectively (P < 0.001). Most often a statistically significant difference between the fezolinetant and placebo group was observed after only 1 week of treatment, demonstrating a very rapid onset.

Study ESN364_HF_205 was a 12-week double-blind, placebo-controlled, parallel-group, multicenter, dose-ranging study to assess the effect of 12-week administration of once daily and twice daily doses of fezolinetant in early postmenopausal women suffering from HF (8 arm study). A total of 356 subjects were randomized into this study with 43 to 45 subjects in each treatment group. There was a clinically relevant treatment effect observed at multiple doses. All groups were significantly different from placebo with respect to mean change in the frequency of moderate to severe VMS at both weeks 4 and 12. The improvement relative to placebo at weeks 4 and 12 was greater than 2 HF per day, indicative of a clinically relevant improvement, for all dose groups except 15 mg twice daily. All groups were significantly different from placebo with respect to mean change in the severity of moderate to severe VMS from baseline to week 4, but only 60 mg twice daily, 90 mg twice daily and 60 mg once daily demonstrated significance at week 12 in this study.

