2.2.2 Dose Rationale

A phase 2b dose-ranging study (ESN364_HF_205) assessing the effects of the potent and selective NK3 antagonist, fezolinetant, on VMS in post-menopausal females was recently completed.

From the ESN364_HF_205 study, 352 subjects were randomized and received at least 1 dose of study drug, 287 (81%) completed the study (placebo: 84%; fezolinetant: 80%).

Discontinuations occurred most commonly for withdrawal of consent (6.7%) and AEs (5.9%).

The 4 co-primary efficacy endpoints for ESN364_HF_205 included the mean change in frequency and severity of moderate-to-severe VMS at week 4 and week 12. VMS frequency and severity at weeks 4 and 12 were reduced in all fezolinetant groups. Differences from placebo in least squares mean changes from baseline in VMS daily frequency at week 4 were -1.9, -3.0, -2.8 and -3.5 for 15, 30, 60 and 90 mg twice daily and -2.3, -3.0 and -2.4 for

30, 60 and 120 mg once daily, respectively (common SE: 0.8; all $P < 0.05$, from a pairwise comparison against placebo without multiplicity adjustment). Differences at week 12 were -1.8, -2.1, -2.3, -2.6 and -2.1, -2.6, -2.1, respectively (common SE: approximately 0.7; all $P < 0.05$ from a pairwise comparison against placebo without multiplicity adjustment). The improvement relative to placebo at weeks 4 and 12 was greater than 2, indicative of a clinically meaningful improvement, for all dose groups except 15 mg twice daily. For HF severity, all treatment groups were statistically significant compared to placebo at week 4, while only the 60 mg twice daily, 90 mg twice daily and 60 mg once daily were statistically different from placebo at week 12. Unlike frequency, a clinically meaningful improvement in HF severity has not been established.

Fezolinetant was generally well-tolerated. No deaths or treatment-related serious adverse events (SAEs) were reported. The rates of TEAEs were comparable across groups and were mostly mild and moderate; however, overall the active dose groups had a higher proportion of AEs reported as treatment-related assessed by the site investigators. Nine subjects had ALT or AST elevations $> 3 \times \text{ULN}$. There were no cases of total bilirubin $> 2 \times \text{ULN}$. Seven of the 9 subjects with transaminase elevations received total daily doses of 120 mg or greater.

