6 STATISTICAL METHODOLOGY

6.1 General Considerations

Continuous data will be summarized descriptively including the number of subjects (n), mean, standard deviation (SD), median, minimum and maximum. Categorical data will be summarized by frequencies and percentages. Percentages by categories will be based on the number of subjects with no missing data, i.e. the percentages for the non-missing categories will add up to 100%.

All statistical comparisons will be conducted using 2-sided tests controlling the overall error rate at the 5% significance level, as described in Section 6.4

All data summarization and analyses will be performed using SAS® on Unix. Specifications for table, figures, and data listing formats can be found in the Tables Listings and Figures (TLF) specifications.

As mentioned in the introduction, this analysis plan describes the analyses of the 12-week double-blind treatment period.

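### If the unstructured MMRM does not converge, the Toeplitz fallback in its usual form assumes one variance for all 12 weeks, which the phase 2b data make doubtful for VMS frequency

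*SAP*

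**What the plan says.** Section 6.4.1.1 of the 12-week SAP models each co-primary endpoint over 12 weekly values. On the covariance it says: "An unstructured covariance structure shared across treatment groups will be used to model the within-patient errors", followed in brackets by "and then Toeplitz if model does not converge". On inference it says: "The Kenward-Roger approximation will be used to estimate denominator degrees of freedom and adjust standard errors". Estimation is by REML. No heterogeneous-variance version of Toeplitz is named, and no empirical (sandwich) standard error. Section 6.1 adds: "All data summarization and analyses will be performed using SAS® on Unix". Protocol 7.4.1.1 specifies the unstructured covariance with no fallback, so the SAP phrase is the only instruction for a model that fails to converge.

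The only week-specific precision in the documents is in Protocol 2.2.2. For the phase 2b difference from placebo in daily frequency, it gives a common standard error of 0.8 at week 4 and, at week 12, "common SE: approximately 0.7". Protocol 1.3.2 describes that study as randomized "with 43 to 45 subjects in each treatment group", and Protocol 2.2.2 reports that 81% completed. For severity, the sample size sections of both documents give only a range of mean differences.

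**The concern.** Under its usual definition, Toeplitz lets the correlation depend on the lag between weeks but uses one common variance. The SAP does not say whether it means this version, but the plain name normally does. If the true variance changes over time, one pooled variance gives standard errors that are too small where variance is high and too large where it is low. Kenward-Roger adjusts for small samples within the chosen structure and takes that structure as correct.

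In phase 2b the frequency standard error fell between weeks 4 and 12, although attrition alone would push it up. That points to falling variance. The fallback would then give a week 4 interval that is too narrow and a week 12 test that is too conservative. A dose succeeds only if all four co-primary endpoints are significant (12-week SAP 6.4), so lost power at week 12 can cost a dose.

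**Working it through.** **1. The plan's own power figure.** Inputs from 12-week SAP section 3: 120 per arm, SD 5, difference -2.0, two-sided 2.5%. SE = 5 × √(2/120) = 0.6455, and 2.0/0.6455 = 3.098. The critical value is 2.241. Power = Φ(3.098 − 2.241) = Φ(0.857) = 80.4% (80.0% with the exact noncentral t), against a stated 79%. The figure is reproduced within rounding.

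**2. What phase 2b implies about the frequency SD.** SD = SE × √(n/2), with 44 per arm taken from the 43 to 45 reported.
- Week 4: 0.8 × √22 = 3.75.
- Week 12 at equal n: 0.7 × √22 = 3.28. The SD ratio is 0.875.
- Week 12 with 36 per arm (81% of 44 = 35.6; an assumption, because n by week is not given): 0.7 × √18 = 2.97. The SD ratio is 0.79.

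Both standard errors are rounded to one decimal, so they stand for 0.75-0.85 and 0.65-0.75. The SD ratio can then run from 0.65/0.85 = 0.76 to 0.75/0.75 = 1.00 at equal n. Multiplying by √(36/44) = 0.905 gives 0.69 to 0.90 with 36 per arm at week 12.

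**3. What a one-variance Toeplitz would do.** The documents give neither the correlations nor the variances at other weeks, so these are assumed. SD falls in a straight line from week 4 to week 12. Over weeks 1-4 it is either flat or on the same line extended back. Three correlation patterns were tried: first-order autoregressive at 0.9, constant at 0.7, and a blend. The 12 × 12 covariance was projected onto the closest one-variance Toeplitz matrix (minimum Kullback-Leibler distance, complete data), and the fitted SD was divided by the true SD.

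One case can be checked by hand, because with constant correlation the fitted variance is close to the average of the 12 weekly variances. Take an SD ratio of 0.875 with SD flat at 1 for weeks 1-4. The squared SDs for weeks 5 to 12 sum to 6.925, so the average is (4 + 6.925)/12 = 0.910 and the fitted SD is 0.954. Week 4: 0.954/1 = 0.954, or 5% too small. Week 12: 0.954/0.875 = 1.090, or 9% too large.

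Across the assumed patterns (flat or straight-line over weeks 1-4):

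| SD ratio, week 12 to week 4 | Week 4 SE | Nominal 5% becomes | Week 12 SE | Nominal 5% becomes |
|---|---|---|---|---|
| 1.00, flat | correct | 5.0% | correct | 5.0% |
| 0.875 | 4-5% too small | 5.9-6.3% | 8-10% too large | 3.1-3.4% |
| 0.79 | 6-9% too small | 6.5-7.3% | 16-19% too large | 2.0-2.3% |

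The error rates are 2 × (1 − Φ(1.96 × SE ratio)). If SD instead rises to week 4 from 0.85 of its week 4 value at week 1, then for the ratios 0.875 and 0.79 the week 4 error grows to 7-13% and the week 12 error shrinks to 3-14%.

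**4. Power at week 12.** With the standard error 9% too large and SD 5 taken as the true week 12 SD, power = Φ(3.098 − 2.241 × 1.09) = Φ(0.655) = 74.4%, against 80.4% with a correct standard error.

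**5. Parameters.** Unstructured has 12 × 13/2 = 78, plain Toeplitz 12, and heterogeneous Toeplitz 12 + 11 = 23. The heterogeneous form contains every covariance assumed above, so it gives an SE ratio of 1.00 at both weeks.

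**The case against.** The strongest reply is that the evidence is thin and the event may never occur. There are two standard errors at one decimal, one of them marked approximate, with no n by week and no statement of the model behind them. At equal n, rounding alone allows no change in variance. All of this stands. A reader might infer that phase 2b demonstrates falling variance; the documents support only that it suggests it. Attrition makes a fall more likely, but the number remaining at week 12 is not given.

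A reader might also infer that all four co-primary standard errors would be wrong. The documents do not support that. With no severity standard error by week, constant variance for severity is unsupported rather than refuted.

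A third tempting reading is that the week 4 error threatens the trial's type I error. Each dose is tested by the largest of its four p-values, so the inflation counts fully only if the drug works on everything except week 4 frequency. Phase 2b points the other way: for 30 mg once daily the differences were -2.3 at week 4 and -2.1 at week 12.

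Nor does the power loss necessarily mean a shortfall against the plan. If SD 5 is the pooled value and the week 12 SE is 9% too large, the true week 12 SD is 5/1.09 = 4.59, and 2.0/(4.59 × √(2/120)) = 3.377. Power is then Φ(3.377 − 2.443) = 82% under the fallback and Φ(3.377 − 2.241) = 87% with a correct standard error. That is above the planned 79%, but still about 5 points lost.

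Finally, nothing in the documents suggests that non-convergence is likely with about 450 women. Even so, the SAP itself provides for it, and the same model is refitted on the per-protocol sets, the COVID-excluded data and 30 imputed datasets (12-week SAP 6.4.1.2). A correct fallback costs almost nothing.

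**Conclusion.** The point holds as a minor one. The named fallback, read in its usual form, assumes a constant variance that the phase 2b frequency data make doubtful, and nothing else in the plan protects the standard errors. If it were used, the frequency standard error would be about 4-9% too small at week 4 and 8-19% too large at week 12. Those ranges take SD ratios of 0.875 and 0.79, variance flat or on a straight line over weeks 1-4, the three assumed correlation patterns and complete data. They are not bounds: rounding allows ratios outside those two values, and constant variance gives no error. The practical cost is mainly power for frequency at week 12, measured against a correct standard error. No claim is made about severity, and none of this arises if the unstructured model converges.

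**What to change.** In 12-week SAP 6.4.1.1, state the fallback order as: unstructured; then heterogeneous Toeplitz, with a separate variance for each week; then plain Toeplitz only if that also fails to converge. Heterogeneous Toeplitz includes plain Toeplitz as a special case, so almost nothing is lost if the variance turns out to be constant. The cost is one phrase in the SAP, one option in the code and 11 more parameters, which is negligible with about 450 women. An empirical standard error would be an alternative, but it would replace the model-based one that Kenward-Roger adjusts, so changing the structure is simpler.

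The spatial power fallback for the key secondary endpoint (12-week SAP 6.4.2) is also a one-variance structure in its usual form and could be reviewed at the same time.

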6.4.1.2 Sensitivity Analysis for Primary Efficacy Endpoints

The following sensitivity analyses will be performed for the primary efficacy endpoints to assess the robustness of the primary analysis.

MMRM model based on PPS populations

Supportive analyses will be carried out for the co-primary efficacy endpoints based on the PPS populations. The data will be analyzed using the same MMRM model as the primary analyses, but the comparison of interest is a particular week within each population (Week 4 when using PPS4, and Week 12 when using PPS12).

Simplified MMRM model

The analysis for each of the co-primary endpoints also will be conducted using a simplified MMRM model with treatment group and week as factors, with baseline measurement as a covariate as well as an interaction of treatment by week and baseline by week.

Discontinuation-reason based multiple imputation

The MMRM analysis that will be used to perform the primary analysis of the primary endpoint assumes that missingness is at random. That is, the model assumes that the trajectory of VMS events over time for subjects who prematurely discontinue is similar to the trajectory for those observed in their own treatment arm which is valid so long as that assumption is reasonable.

Discontinuation-reason based multiple imputation (MI) will be used to examine the sensitivity of the primary analysis results to departures from that underlying assumption and will assess a situation where data for subjects who discontinue early follow a pattern which is missing not at random. Specifically, MI will be used for imputation of missing data, using "Jump to Reference" algorithm (where placebo is the reference group) [Carpenter et al. 2013] for subjects who discontinue active treatment due to AEs (AE reported as primary study drug treatment status in the End of Treatment eCRF). The analysis will be implemented using the general three-step process (imputation phase, followed by analysis phase, followed by pooling phase) described in O'Kelly and Ratitch, 2014.

- 1. The imputation phase will implement MI via sequential modelling for the "Jump to Reference" algorithm. In particular, when implementing the "Jump to Reference" algorithm via sequential modelling, this means that only baseline values are used in the imputation of missing values for subjects in the fezolinetant 30 mg or 45 mg groups who discontinue due to AEs (this variation of the "Jump to Reference" algorithm is also referred to as the "Unconditional Reference" approach). The imputation phase will generate M imputed datasets, where M=30.
- 2. The analysis phase will perform the primary MMRM analysis model of the primary efficacy endpoint as described in Section 6.4.1.1 for each of the *M* imputed datasets.
- 3. Rubin's rules will be used to generate an overall set of pooled results which combines the analysis results from the *M* imputed datasets.

The overall set of pooled results will present:

- Least squares (LS) mean estimates, SE and 2-sided 90% confidence interval (CI) for mean change from baseline to Week 12 within a treatment group (fezolinetant 30 mg or 45 mg, placebo),
- The difference in LS means for fezolinetant 30 mg or 45 mg versus placebo, SE for the difference and 2-sided 90% CI for the difference at Week 4 and Week 12,
- Two-sided p-value for fezolinetant 30 mg or 45 mg versus placebo at Week 4 and Week 12, obtained using the difference in the LS means.
- Descriptive summary statistics at Week 4 and Week 12 will be derived using the mean of the *M* imputed datasets.

COVID-19 Impact

The primary analysis will be repeated by excluding diary data that are impacted by COVID-19, which includes the diary data recorded after the subjects were diagnosed of COVID-19, after study drug discontinuation due to COVID-19, and during dose interruption due to COVID-19.

